## 7.10. **Concomitant Medications**

Concomitant medications will include all medications taken while the patient on study drug and are defined as any medications other than the study drug with stop dates on or after the first dose date. Medications with partial or missing stop dates will be assigned as concomitant medications unless the stop dates are apparently prior to the first dose date.

All concomitant medications will be coded using the WHO Drug Dictionary version March 2014 enhanced B2 format. The incidence of concomitant medications will be summarized using descriptive statistics by therapeutic class and preferred term. Patients are counted only once in each therapeutic class category, and only once in each preferred term category. Concomitant medications will include all medications taken while the patient takes study drug.

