3.11.3. Procedures During Double-Blind Treatment Period (Day 1 Through Day 29 Visit)

The start of study drug treatment occurs on the randomization visit (visit 3, day 1), as detailed in Section 3.11.2. Study drug treatment continues until the evening of day 28.

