3.11.4. Procedures After Study Drug Treatment

3.11.4.1. Follow-up Period (After the Week 4 Visit)

At the week 4 visit (visit 5, day 29), patients who completed the double-blind treatment period will enter a 4-week follow-up period, during which they will not use study drug. They should be instructed to return to their primary care physician to resume therapy deemed appropriate for their PHN.

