3.11.4.2. Follow-up Visit or ET visit (Visit 6, Day 57 [± 3])

At the end of the follow-up period (visit 6, day 57 ± 3), patients will return to the study site for the follow-up visit. This visit will be the final visit of the study. Activities at the follow-up visit will include the following:

- perform adverse event inquiry
- review medications taken since previous visit

- perform clinical laboratory tests (serum chemistry, hematology, and urinalysis)
- perform vital signs measurements
- perform physical examination (including body weight)
- perform 12-lead ECG (all ECGs taken in triplicate tracings obtained at least 1 minute apart [with an upper limit of 5 minutes apart])
- obtain urine pregnancy test (women of child-bearing potential only)
- evaluate area of PHN pain for dermal irritation

Activities performed at the ET visit only will include the following:

- obtain NPSI, DSIS, NePIQoL, and PGIC assessments
- measure maximal intensity of brush-evoked allodynia and maximal intensity of punctate-evoked hyperalgesia
- collect rescue medication (if prior to visit 5)
- review and record rescue medication use (if any) as concomitant medication, not using eDiary
- review eDiary and review eDiary data via website, including the following data recorded by the patient the previous evening (if prior to visit 5):
 - date/time of study drug application
 - rescue pain medication usage for PHN
 - worst daily pain intensity (NRS) in the evening
- collect eDiary (if prior to visit 5)
- review study and rescue drug compliance
- collect study drug (if prior to visit 5)

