5.3. Prior and Concomitant Therapy or Medication

Any prior or concomitant therapy or medication that a patient has had within 90 days before study drug administration and up to the end of the study period, including follow-up, will be recorded on the CRF. Generic or trade name, indication, and dosage will be recorded. The Sponsor will encode all therapy and medication according to the World Health Organization drug dictionary (WHO Drug).

The following medications will not be allowed during this study:

- Oral analgesics
- Topical analgesics, including lidocaine (gels, creams and patches) and capsaicin patches
- Rescue pain medication except permitted acetaminophen rescue
- Class Ic anti-arrhythmic drugs such as flecainide or propafenone

At each clinic visit after the screening visit, the investigator will ask patients whether they have taken any medications (other than study drug), including OTC medications, vitamins, or herbal or nutritional supplements, since the previous visit. Indication, dosage, and start and end dates should be entered on the CRF.

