9.8.2. Safety Analysis

All adverse events will be coded using the Medical Dictionary for Regulatory Activities (MedDRA). Each patient will be counted only once in each preferred term or system organ class (SOC) category for the analyses of safety. Summaries will be presented for all adverse events (overall and by severity), adverse events determined by the investigator to be related to study treatment (ie, reasonable possibility; see Section 7.1.4) (adverse events defined as related or with missing relationship will be summarized overall and by severity), serious adverse events, and adverse events causing withdrawal from the study. Summaries will be presented by treatment group and for all patients. Patient listings of serious adverse events and adverse events leading to withdrawal will be presented.

Changes in laboratory and vital signs measurement data will be summarized descriptively. All values will be compared with prespecified boundaries to identify potentially clinically significant changes or values, and such values will be listed.

The use of concomitant medications will be summarized by therapeutic class using descriptive statistics. Concomitant medications will include all medications taken while the patient is treated with study drug.

For continuous variables, descriptive statistics (n, mean, standard deviation, standard error, median, minimum, and maximum) will be provided for actual values and changes from baseline to each time point. For categorical variables, patient counts and percentages will be provided. Descriptive summaries of serious adverse events, patient withdrawals due to adverse events, and potentially clinically significant abnormal values (clinical laboratory or vital signs) based on predefined criteria will also be provided.

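### SAP 7.10 puts no upper limit on start date, so therapy resumed after the last dose is pooled with on-treatment use in Table 15.3.25

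*SAP*

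**What the plan says.** SAP 7.10 opens with the idea of use during study drug treatment and closes with it again: "Concomitant medications will include all medications taken while the patient takes study drug". Protocol 9.8.2 agrees: "Concomitant medications will include all medications taken while the patient is treated with study drug".

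Between those statements is the rule a programmer would apply. Concomitant medications "are defined as any medications other than the study drug with stop dates on or after the first dose date". It continues: "Medications with partial or missing stop dates will be assigned as concomitant medications", except where the stop was apparently before first dose. Neither sentence compares the start date with the last dose.

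The surrounding provisions are:

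- Protocol 3.11.3: "Study drug treatment continues until the evening of day 28".
- Protocol 3.11.4.1, on completers entering the 4-week follow-up without study drug: "They should be instructed to return to their primary care physician to resume therapy deemed appropriate for their PHN".
- Protocol 5.3: therapy from 90 days before study drug "up to the end of the study period, including follow-up, will be recorded on the CRF". Start and end dates are collected.
- Protocol 3.11.4.2, at visit 6 (day 57 ±3): "review medications taken since previous visit".

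SAP 5.5 defines prior medications and SAP 7.10 concomitant ones; there is no post-treatment category. Table 15.3.25 is by therapeutic class and treatment group, with no split by period in its title or in the text.

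**The concern.** The rule is wider than the concept it is meant to implement. It separates prior from concomitant medication at first dose, but has no matching boundary at last dose.

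The design makes this matter. Oral and topical analgesics are barred during the study under Protocol 5.3, yet completers are directed back to PHN therapy once treatment ends, while medications are still being recorded. Resumed therapy will often be ongoing at visit 6, and an absent stop date also defaults to concomitant. Table 15.3.25 would then combine a period in which these drugs were barred with one in which resuming them was expected. Each patient counts once per class, so the two uses cannot be separated in the table.

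At stake is how well one descriptive safety table shows on-treatment medication use by arm. Concomitant medication use is a named safety measure, compared with placebo.

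The protocol's wording does not settle the matter. The SAP preface gives the SAP precedence where the two differ, and SAP 10, which lists changes from the protocol, does not mention this one.

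**Working it through.** The plan states no figure on this point, so there is none to reproduce. The check has two parts.

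**1. Applying the rule to example records.** First dose is day 1 and last dose day 28. The SAP rule is: stop ≥ day 1, or stop missing. The bounded rule adds: start ≤ day 28.

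| Example record | SAP rule | Bounded rule |
|---|---|---|
| Started long before day 1, stopped day −12 | no | no |
| Long-standing drug, ongoing | yes | yes |
| Taken days 10 to 14 | yes | yes |
| Started day 30, stopped day 50 | yes | no |
| Started day 30, ongoing at visit 6 | yes | no |

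Only the last two rows change. Both began after study drug ended, so neither fits the concept stated in SAP 7.10 or Protocol 9.8.2. Genuine on-treatment use is classified the same way under both rules.

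**2. Illustrating the dilution.** Let p be the true proportion of an arm using a drug class on treatment, c the proportion completing, and r the proportion of completers not already counted who take up that class after day 29. Because a patient counts once per class, the SAP rule displays

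p + (1 − p) × c × r.

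With c and r equal across arms, a true difference d is displayed as d × (1 − c × r).

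The value c = 0.80 comes from the plan's 20% dropout assumption (88 of 110 per arm). The values of p and r are assumptions; the documents give neither. Take p = 5% and 15%, so d = 10 points. At r = 50%:

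- 0.05 + 0.95 × 0.80 × 0.50 = 0.43
- 0.15 + 0.85 × 0.80 × 0.50 = 0.49

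| Assumed r | Displayed, lower arm | Displayed, higher arm | Displayed difference |
|---|---|---|---|
| 10% | 12.6% | 21.8% | 9.2 points |
| 25% | 24.0% | 32.0% | 8.0 points |
| 50% | 43.0% | 49.0% | 6.0 points |
| 75% | 62.0% | 66.0% | 4.0 points |

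The bounded rule displays 5% and 15% in every row.

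The dilution is this regular only if completion and resumption are equal across arms. If on-treatment use is equal but completion differs, the displayed arms differ by (1 − p) × r × (c₁ − c₂), taking c₁ and c₂ as the two completion rates. Completers have about four weeks of recorded time off drug. Patients who stop early have a termination visit within two weeks of last dose (Protocol 4.4), often their last visit.

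**The case against.** The best defence is that SAP 7.10 does not rest on the stop date alone. It states the on-drug concept twice, and on a sympathetic reading that is a condition in its own right, with the stop date serving only to separate concomitant from prior medication. This stands as far as it goes: the defect is a conflict between concept and rule, not a missing concept. But the sentence that says how the category is defined is the unbounded one, and following it literally misclassifies post-treatment starts.

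Second, the safety objective covers concomitant medication use throughout the study, so follow-up medication belongs in the report. That also stands. It argues for showing follow-up use, but not for showing it under a label that means on study drug.

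Two stronger readings are tempting:

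- **That prohibited use during treatment is hidden.** The documents do not support this. Protocol 11.1.2 makes use of prohibited medication a protocol violation recorded on the CRF. SAP 5.7, Table 15.1.7 and Listing 16.2.2 report violations, and Listing 16.2.8.16 covers prior and concomitant medications by patient. On-treatment use also remains in Table 15.3.25, though pooled. These sources do not replace the table, since violations are summarized by violation category with no stated breakdown by drug class.
- **That analgesic use in the primary endpoint window is obscured and the efficacy result weakened.** Week 4 is days 22 to 28, and even a corrected Table 15.3.25 would cover days 1 to 28. Rescue acetaminophen is recorded in the eDiary, and SAP 3.4 and 6.2.3 handle it separately. No visible efficacy analysis uses the 7.10 definition.

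**Conclusion.** The concern holds in limited form. As written, the rule in SAP 7.10 counts medication started after the last dose as concomitant, contrary to the section's own concept and to Protocol 9.8.2. Table 15.3.25 would therefore pool on-treatment use with therapy resumed in follow-up. This follows from the text and needs no assumption about rates.

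The size does rest on assumptions. With 80% completion in each arm and 10% to 75% of eligible completers taking up the class, a true 10-point difference would be displayed as 9.2 down to 4.0 points. The documents give no resumption rate. The instruction to resume appropriate therapy fixes no drug or class, so no count of misclassified patients can be derived, and those patients need not fall in one row of the table.

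The effect is confined to one descriptive safety table. It is still worth correcting before the randomization codes are opened, because a stated rule gives a wrong classification and the SAP takes precedence over the protocol.

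**What to change.** In SAP 7.10, replace the derivation with three statements:

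1. A medication is concomitant if its start date is on or before the last dose date **and** its stop date is on or after the first dose date, or it is ongoing or has a missing stop date. Retain the existing treatment of partial stop dates.
2. A medication with a partial or missing start date stays concomitant unless the available part shows a start after the last dose.
3. Medications started after the last dose are tabulated separately as post-treatment, by therapeutic class and treatment group, so that use throughout the study is still reported.

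The cost is a short SAP edit, one added programming condition and one further table. No new data are needed: the CRF holds medication start and end dates, and SAP 7.2 already derives the first and last days of study drug from the eDiary. Genuine on-treatment use with known dates is classified as before.

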## **8. PHARMACOKINETIC/PHARMACODYNAMIC ANALYSIS**

The population pharmacokinetic analysis will be detailed in a separate analysis plan, and results will be reported separately from the main study results.

The pharmacodynamic variables of maximal intensity of patients' brush-evoked allodynia and maximal intensity of patients' punctate-evoked hyperalgesia are detailed in section 6.3, Secondary Efficacy Variables and Analyses. Exploratory analyses may be reported separately from the main study results.

## **9. STATISTICAL SOFTWARE**

All data listings, summaries, and statistical analyses will be generated using SAS® version 9.3 or higher.

## **10. CHANGES TO PROTOCOL SPECIFIED ANALYSES**

Protocol Section 9.5.2, Demographics and Baseline Characteristics, states that treatment groups will be compared for all categorical variables using a Pearson chi-square (or Fisher's exact test if cell sizes are too small). No comparisons will be done for demographic variables.

Protocol Section 9.6.1.1, Primary Efficacy Analysis, states that the MMRM model will analyze change from baseline in the weekly average of the daily average NRS scores at weeks 2 and 4 as the dependent variable. The change from baseline in the weekly average of the daily average NRS scores at weeks 1, 2, 3, and 4 will be used. Weeks 1 and 3 will also be included in the model.

Protocol Section 9.6.1.3, Secondary Efficacy Analysis, states that the time to reach  $\geq 30\%$  improvement in weekly average NRS scores from baseline will be summarized using descriptive statistics. This analysis will be reporting using Kaplan-Meier.

## 12. LIST OF SUMMARIES AND LISTINGS

### 12.1. Summary Tables

Summary number	Title	Population
15.1.1	Patient Disposition by Treatment Group	All Patients
15.1.2	Demographics by Treatment Group	Intent-to-Treat Population
15.1.3	Childbearing Potential by Treatment Group	Intent-to-Treat Population
15.1.4	General Medical History by Treatment Group	Intent-to-Treat Population
15.1.5	Prior Medications by Therapeutic Class, Preferred Term, and Treatment Group	Intent-to-Treat Population
15.1.6	Electrocardiogram Findings at Baseline by Treatment Group	Intent-to-Treat Population
15.1.7	Protocol Violations by Treatment Group	Intent-to-Treat Population
15.2.1.1	Summary of Change from Baseline in Weekly Average of the Daily Average NRS Pain Scores	Full Analysis Set
15.2.1.2	Summary of Change from Baseline in Weekly Average of the Daily Average NRS Pain Scores	Per Protocol Population
15.2.1.3	Sensitivity Analysis of Change from Baseline to Week 4 in Weekly Average of the Daily Average NRS Pain Scores	Full Analysis Set
15.2.2.1	Summary of Change from Baseline in Weekly Average of Average NRS Pain Score Recorded in the Evening	Full Analysis Set
15.2.2.2	Summary of Change from Baseline in Weekly Average of Average NRS Pain Score Recorded in the Evening	Per Protocol Population
15.2.3.1	Summary of Change from Baseline in Weekly Average of Average NRS Pain Score Recorded in the Morning	Full Analysis Set
15.2.4.1	Summary of Change from Baseline in Weekly Average of Worst NRS Pain Score Recorded in the Evening	Full Analysis Set
15.2.5.1	Responder Rate in Weekly Average of the Daily Average NRS Pain Scores at Week 4	Full Analysis Set
15.2.5.2	Responder Rate in Weekly Average of the Daily Average NRS Pain Scores at Week 4	Per Protocol Population
15.2.6.1	Summary of Change from Baseline in Neuropathic Pain Symptom Inventory (NPSI)	Full Analysis Set
15.2.7.1	Summary of Change from Baseline to Week 4 in Neuropathic Pain Impact on Quality of Life (NePIQoL)	Full Analysis Set
15.2.8.1	Summary of PGIC Scores after 2 Weeks and 4 Weeks of Study Drug Treatment	Full Analysis Set
15.2.8.2	Summary of PGIC Scores after 2 Weeks and 4 Weeks of Study Drug Treatment	Per Protocol Population

Summary number	Title	Population
15.2.9.1	Summary of Change from Baseline in Daily Sleep Interference Scale (DSIS)	Full Analysis Set
15.2.9.2	Summary of Change from Baseline in Daily Sleep Interference Scale (DSIS)	Per Protocol Population
15.2.10.1	First Time to Reach 30% or More Sustained Improvement in Weekly Average of the Daily Average NRS Pain Scores	Full Analysis Set
15.2.11.1	Summary of Change from Baseline in Maximal Intensity of Brush-Evoked Allodynia as Measured on 11-point NRS	Full Analysis Set
15.2.12.1	Summary of Change from Baseline in Maximal Intensity of Punctate-Evoked Hyperalgesia as Measured on 11-point NRS	Full Analysis Set
15.2.13.1		Full Analysis Set
15.2.13.2		Per Protocol Population
15.2.13.3		Full Analysis Set
15.2.13.4		Full Analysis Set
15.2.13.5		Full Analysis Set
15.2.13.6		Full Analysis Set
15.2.13.7		Per Protocol Population
15.2.13.8		Full Analysis Set
15.2.13.9		Full Analysis Set
15.2.13.10		Full Analysis Set
15.2.13.11		Full Analysis Set
15.2.13.12		Full Analysis Set
15.2.13.13		Full Analysis Set
15.2.13.14		Full Analysis Set

Summary number	Title	Population
15.2.14	[REDACTED]	Full Analysis Set
15.2.15.1	[REDACTED]	Full Analysis Set
15.2.15.2	[REDACTED]	Full Analysis Set
15.2.15.3	[REDACTED]	Full Analysis Set
15.2.15.4	[REDACTED]	Full Analysis Set
15.2.16	Association of CYP3A4 and CYP2C19 with Response Variables	Full Analysis Set
15.3.1.1	Study Drug Exposure by Treatment Group	Safety Analysis Set
15.3.1.2	Study Drug Compliance by Treatment Group	Safety Analysis Set
15.3.1.3	Pharmacokinetic Plasma Concentrations	Safety Analysis Set
15.3.2	Treatment Emergent Adverse Events by System Organ Class, Preferred Term, and Treatment Group	Safety Analysis Set
15.3.3	Treatment Emergent Adverse Events by System Organ Class, Preferred Term, Severity, and Treatment Group	Safety Analysis Set
15.3.4	Treatment-Related Adverse Events by System Organ Class, Preferred Term, and Treatment Group	Safety Analysis Set
15.3.5	Treatment-Related Adverse Events by System Organ Class, Preferred Term, Severity, and Treatment Group	Safety Analysis Set
15.3.6	Treatment Emergent Adverse Events by System Organ Class, Preferred Term, Causality, and Treatment Group	Safety Analysis Set
15.3.7	Treatment Emergent Serious Adverse Events by System Organ Class, Preferred Term, and Treatment Group	Safety Analysis Set
15.3.8	Treatment Emergent Adverse Events Causing Discontinuation From the Study by System Organ Class, Preferred Term, and Treatment Group	Safety Analysis Set
15.3.9	Treatment Emergent Non-Serious Adverse Events by System Organ Class, Preferred Term, and Treatment Group	Safety Analysis Set
15.3.10	Serum Chemistry Laboratory Tests Results and Changes From Baseline to Each Visit by Treatment Group	Safety Analysis Set
15.3.11	Hematology Laboratory Tests Results and Changes From Baseline to Each Visit by Treatment Group	Safety Analysis Set
15.3.12	Urinalysis Laboratory Tests Results and Changes From Baseline to Each Visit by Treatment Group	Safety Analysis Set
15.3.13	Serum Chemistry Laboratory Tests Results Shifts From Baseline to Each Visit by Treatment Group	Safety Analysis Set

Summary number	Title	Population
15.3.14	Hematology Laboratory Tests Results Shifts From Baseline to Each Visit by Treatment Group	Safety Analysis Set
15.3.15	Urinalysis Laboratory Tests Results Shifts From Baseline to Each Visit by Treatment Group	Safety Analysis Set
15.3.16	Serum Chemistry Laboratory Tests Potentially Clinically Significant Abnormal Results by Treatment Group	Safety Analysis Set
15.3.17	Hematology Laboratory Tests Potentially Clinically Significant Abnormal Results by Treatment Group	Safety Analysis Set
15.3.18	Urinalysis Laboratory Tests Potentially Clinically Significant Abnormal Results by Treatment Group	Safety Analysis Set
15.3.19	Vital Signs Values and Changes From Baseline to Each Visit by Treatment Group	Safety Analysis Set
15.3.20	Vital Signs Potentially Clinically Significant Abnormal Values by Treatment Group	Safety Analysis Set
15.3.21	Electrocardiogram Findings Shifts From Baseline to Overall and Each Visit by Treatment Group	Safety Analysis Set
15.3.22	Electrocardiogram Variables Results and Changes From Baseline to Each Visit by Treatment Group	Safety Analysis Set
15.3.23	Dermal Irritation Finding at Each Visit by Treatment Group	Safety Analysis Set
15.3.24	Summary of Time (days) to First Application Site Skin Irritation by Treatment Group	Safety Analysis Set
15.3.25	Concomitant Medications by Therapeutic Class and Treatment Group	Safety Analysis Set

## 12.2. Individual Patient Data Listings

Listing Number	Title	Population
16.2.1.1	Patient Disposition by Treatment Group	Intent-to-Treat Population
16.2.1.2	Patients Who Did Not Meet Screening Criteria	
16.2.2	Protocol Violations by Treatment Group	Intent-to-Treat Population
16.2.4.1	Demographics by Treatment Group	Intent-to-Treat Population
16.2.4.2	Childbearing Potential by Treatment Group (Females Only)	Intent-to-Treat Population
16.2.4.3	Telephone Contact and Patient Continuation at Washout Period by Treatment Group	Intent-to-Treat Population
16.2.4.4	Medical History by Treatment Group	Intent-to-Treat Population
16.2.5.1	Study Drug Record by Treatment Group	Intent-to-Treat Population
16.2.5.2	Study Drug Accountability by Treatment Group	Intent-to-Treat Population
16.2.5.3	Rescue Drug Accountability by Treatment Group	Intent-to-Treat Population
16.2.5.4	Rescue Drug Record by Treatment Group	Intent-to-Treat Population
16.2.6.1	Numerical Rating Scale (NRS) Pain Scores by Treatment Group	Intent-to-Treat Population

Listing Number	Title	Population
16.2.6.2	Neuropathic Pain Symptom Inventory (NPSI) by Treatment Group	Intent-to-Treat Population
16.2.6.3	Neuropathic Pain Impact on Quality of Life (NePIQoL) by Treatment Group	Intent-to-Treat Population
16.2.6.4	Patient Global Impression of Change (PGIC) by Treatment Group	Intent-to-Treat Population
16.2.6.5	Daily Sleep Interference Scale (DSIS) by Treatment Group	Intent-to-Treat Population
16.2.6.6	Brush-Evoked Allodynia and Punctate-Evoked Hyperalgesia by Treatment Group	Intent-to-Treat Population
16.2.6.7	[REDACTED]	Intent-to-Treat Population
16.2.6.8	Genetic Variables by Treatment Group	Intent-to-Treat Population
16.2.7.1	Adverse Events by Treatment Group	Intent-to-Treat Population
16.2.7.2	Deaths by Treatment Group	Intent-to-Treat Population
16.2.7.3	Serious Adverse Events by Treatment Group	Intent-to-Treat Population
16.2.7.4	Adverse Events Causing Discontinuation From the Study by Treatment Group	Intent-to-Treat Population
16.2.8.1	Laboratory Reference Ranges	
16.2.8.2	Serum Chemistry Laboratory Tests Results by Treatment Group	Intent-to-Treat Population
16.2.8.3	Hematology and Coagulation Laboratory Tests Results by Treatment Group	Intent-to-Treat Population
16.2.8.4	Urinalysis Laboratory Tests Results by Treatment Group	Intent-to-Treat Population
16.2.8.5	Urine Drug Screen Results by Treatment Group	Intent-to-Treat Population
16.2.8.6	Pregnancy Test Results by Treatment Group (Females Only)	Intent-to-Treat Population
16.2.8.7	Serum Chemistry Laboratory Tests Potentially Clinically Significant Abnormal Results by Treatment Group	Intent-to-Treat Population
16.2.8.8	Hematology Laboratory Tests Potentially Clinically Significant Abnormal Results by Treatment Group	Intent-to-Treat Population
16.2.8.9	Urinalysis Laboratory Tests Potentially Clinically Significant Abnormal Results by Treatment Group	Intent-to-Treat Population
16.2.8.10	Treatment Schedule	Intent-to-Treat Population
16.2.8.11	Vital Signs Values by Treatment Group	Intent-to-Treat Population
16.2.8.12	Vital Signs Potentially Clinically Significant Abnormal Values by Treatment Group	Intent-to-Treat Population
16.2.8.13	Electrocardiogram Findings by Treatment Group	Intent-to-Treat Population
16.2.8.14	Electrocardiogram Variable Results by Treatment Group	Intent-to-Treat Population
16.2.8.15	Dermal Irritation Evaluation by Treatment Group	Intent-to-Treat Population
16.2.8.16	Prior and Concomitant Medications by Treatment Group	Intent-to-Treat Population
16.2.8.17	Pharmacokinetic Plasma Concentrations	Intent-to-Treat Population

Listing Number	Title	Population
16.2.8.18	Adverse Events for Patients Who Did Not Meet Screening Criteria	

